9.1. Adverse Events

The timeframes for collecting and reporting the safety information are provided in Table 7.

Table 7 Timeframes for collecting and reporting of safety information

Event	Timing of reporting
Local and systemic solicited events	Day 1 through Day 7 following each study intervention administration
Unsolicited AEs	Day 1 through Day 30 following each study intervention administration
AEs/SAEs leading to withdrawal from the study	Day 1 following study intervention administration through Phone Contact 2 study conclusion
All SAEs including SAEs related to the study intervention	Day 1 following study intervention administration through Phone Contact 2 study conclusion
AEs/SAEs related to study participation or SAEs related to concurrent GlaxoSmithKline medication/vaccine	Enrollment (i.e., signing ICF) through Phone Contact 2 study conclusion
IMCs, AESIs, COVID-19 cases, and in HZ/su and mRNA-1273 booster cohort only, also pIMDs and suspected HZ episodes	Day 1 following study intervention administration through Phone Contact 2 study conclusion
Pregnancy	Day 1 through Phone Contact 2 study conclusion

Withdrawals due to solicited AEs, both local and systemic, unsolicited AEs, and SAEs will be presented in a listing.

9.1.1. Solicited Adverse Events

Solicited AEs are pre-specified local and systemic adverse events. Solicited AEs will be collected through 7 days following each vaccination. Solicited AEs with onset during the 7-day solicitation period that continue beyond the 7-day period will be reported as solicited AEs. The solicited AEs will be collected using the diary eCRFs.

Participant's compliance with respect to the diary card based on the Exposed Set will be determined separately for local and systemic events for the following:

- Number of participants who did not present diary data at all
- Number of participants who completed diary card, regardless of visit
- Number of participants who completed diary card for each day of the first 7 days post any vaccination (i.e., Day 1, Day 2, Day 3, Day 4, Day 5, Day 6 and Day 7)

A sensitivity analysis to exclude participants who may not have acceptable diary data or certain missing diary records may be performed.

Per the study design and diary forms, participants who receive the administration of the mRNA-1273 booster vaccine on Day 1, have until Day 14 (Week 2) to receive the next vaccine administration. As such, all solicited systemic AEs that occurred on or after mRNA-1273 booster vaccine but prior to HZ/su or Flu D-QIV vaccine administration on Day 14 (Week 2) are deemed to be attributable to the mRNA-1273 booster vaccine. For participants in the sequential groups (HZ/suSeq, FluD-QIVSeq), the diary forms are re-set at the time of first HZ/su or Flu D-QIV vaccination on Day 14 (Week 2) to collect solicited systemic AEs that are either ongoing from mRNA-1273 booster vaccine from Day 1 or occurred on or after the first HZ/su or Flu D-QIV vaccination on Day 14 (Week 2). The diary data is therefore setup to ensure that any solicited systemic AE attributable to each of the following vaccines only: mRNA-1273 booster, first HZ/su, second HZ/su or Flu D-QIV, can be determined depending on the time of the AE relative to the time of each vaccine administration, and prior to the date of any subsequent vaccination. Solicited local AEs are collected in separate diaries per vaccine received and will be attributed to the appropriate based on the diary used.

For data analysis purposes, the CoAd groups (HZ/suCoAd, FluD-QIVCoAd) will be presented as a single column, with the exception of the HZ/suCoAd group that certain selected outputs will be displayed by the first and second HZ/su vaccine doses respectively.

For the sequential groups (HZ/suSeq, FluD-QIVSeq), data will be presented by the individual vaccines as follows:

- A column for mRNA-1273 booster vaccine on Day 1,
- A column for either HZ/su or FluD-QIV vaccine on Day 14 (Week 2) depending on the sequential group,

- A column labelled “Overlapping” to count participants with events that occurred on or after post mRNA booster vaccine dose given at Day 1 and are ongoing after receiving the first HZ/su or Flu D-QIV at Day 14 (Week 2)
- A column labelled either “mRNA-1273 or HZ/su” or “mRNA-1273 or Flu D-QIV” depending on the sequential group, that counts the number of events that each participant experienced under mRNA-1273 or HZ/su vaccine for HZ/SuSeq group or under mRNA-1273 or Flud-QIV vaccine for FluD-QIVSeq group. For participants with overlapping AEs, their events are counted once at maximum severity for any vaccination.

In addition, and specifically for the HZ/su groups (HZ/suSeq, HZ/suCoAd), selected outputs will be displayed by the first and second HZ/su vaccine doses administered within each HZ/suSeq and HZ/suCoAd treatment groups respectively.

The duration of each solicited adverse event will be calculated following the process below:

- the diary data is setup in Study Data Tabulation Model (SDTM) to capture separately events that occurred within the first 7 days and events that occurred longer than 7 days. The 2 datasets are set together.
- Then for each solicited AE that occurred following each vaccination, duration is calculated as sum of the unique number of days of the solicited AE with greater than zero grade

The following specific solicited adverse events will be assessed.

Local solicited AEs:

- Pain
- Redness
- Swelling
- Pruritus
- Axillary (underarm) swelling or tenderness ipsilateral to the injection site

Systemic solicited AEs:

- Fatigue
- Myalgia
- Headache
- Shivering/chills
- Fever
- Gastrointestinal (GI) symptoms (nausea, vomiting, diarrhea and/or abdominal pain). Each symptom under GI will be presented separately and then collectively as GI. For intensity for GI, the highest intensity among all these 4 symptoms will be used. For example – if a subject experiences grade 1 nausea, grade 2 vomiting, grade 3 diarrhea and grade 2 abdominal pain, then the intensity for GI for the subject will be presented as the highest, i.e., grade 3.

- Arthralgia

The solicited AEs will be MedDRA coded to the following SOCs/PTs for a summary by SOCs and PTs combining solicited and unsolicited AEs for all study groups (HZ/suSeq, HZ/suCoAd, FluD-QIVSeq, FluD-QIVCoAd).

Solicited AE	System Organ Class Code	System Organ Class	Preferred Term Code	Preferred Term
Abdominal Pain	10017947	Gastrointestinal disorders	10000081	Abdominal pain
Arthralgia	10028395	Musculoskeletal and connective tissue disorders	10003239	Arthralgia
Chills	10018065	General disorders and administration site conditions	10008531	Chills
Diarrhoea	10017947	Gastrointestinal disorders	10012735	Diarrhoea
Fatigue	10018065	General disorders and administration site conditions	10016256	Fatigue
Headache	10029205	Nervous system disorders	10019211	Headache
Injection Site Erythema	10018065	General disorders and administration site conditions	10022061	Injection site erythema
Injection Site Induration/ Swelling	10018065	General disorders and administration site conditions	10053425	Injection site swelling
Injection Site Pain	10018065	General disorders and administration site conditions	10022086	Injection site pain
Myalgia	10028395	Musculoskeletal and connective tissue disorders	10028411	Myalgia
Nausea	10017947	Gastrointestinal disorders	10028813	Nausea
Pruritus	10040785	Skin and subcutaneous tissue disorders	10022093	Injection site pruritus
Underarm Gland Swelling or Tenderness	10005329	Blood and lymphatic system disorders	10025197	Lymphadenopathy

Vomiting	10017947	Gastrointestinal disorders	10047700	Vomiting
Fever	10018065	General disorders and administration site conditions	10037660	Pyrexia

The number and percentage of participants with at least 1 solicited local event, with at least 1 solicited systemic event and any solicited event as well as each solicited local and solicited systemic AE (within onset within Days 1-7) will be tabulated with exact 95% CIs, for each vaccination visit and overall for all study groups (HZ/suSeq, HZ/suCoAd, FluD-QIVSeq, FluD-QIVCoAd). Similar summaries will be provided for participants with Grade 3 events, medically attended solicited local events, and medically attended solicited systemic events. These summaries will be presented for all the subgroups defined in Section 4.4.

The duration in days of the solicited AEs, both local (for each vaccine separately) and systemic, with onset within 7-days following each vaccination visit and overall (total duration) will be calculated and summarized by mean, median, standard deviation, and range. Similar summaries will be provided for participants with Grade 3 events. These summaries will be presented for age strata subgroups defined in Section 4.4.

In addition, the following below will be presented:

- The percentage of subjects with solicited local adverse events lasting longer than 7 days and duration in days (total) of solicited local adverse events lasting longer than 7 days following each vaccination visit
- The percentage of subjects with solicited systemic adverse events lasting longer than 7 days and duration in days (total) of systemic adverse events lasting longer than 7 days following each vaccination visit
- Both of the above summaries will be presented for age strata subgroups defined in Section 4.4.
- The number of each systemic adverse event (any, grade 3 and medically attended) following Dose 1 of HZ/su or Flu D-QIV and mRNA-1273 vaccination for all groups. For example, if a participant has 2 or more recorded events of the same type then each event is counted.

Separate individual data listings for solicited local adverse events and solicited systemic events will be provided.

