Blood sampling for antibody determination		Refer to Table 2 for blood sampling schedule for each group (●)									
HZ lesion sample (HZ/su and mRNA-1273 booster cohort only)	Unscheduled visits (●)									Refer to Table 3 for procedures to be followed	
Record any concomitant medications/vaccinations		●	●	●	●	●	●	●	●		
Record any intercurrent medical conditions (IMC)		●	●	●	●	●	●	●	●		
Phone contact for safety follow-up								●	●		

CONFIDENTIAL

217670 (ZOSTER-091)
Protocol Amendment 1 Final

Type of contact	Pre-Vacc	Visit 1	Visit 2	Visit 3	Visit 4	Visit 5	Visit 6	Phone Contact 1	Phone Contact 2	Notes	
Timepoint	-7 days	Day 1	Week 2	Week 4	Week 6	Week 10	Week 14	6 weeks post last dose	24 weeks post last dose		
			Week 4	Week 8	Week 12						
			Week 2	Week 4	Week 6						
			Week 4								
Training participants to recognize signs and symptoms of HZ (HZ/su and mRNA-1273 booster cohort only)		○	○	○	○	○	○				
Recording of solicited AEs: onset post-study intervention administration (day of and following 6 days)		Refer to Table 2 for the schedule for each group (●)									
Review/Return of eDiary		○	○	○	○	○	○				
Recording of non-serious AEs within 30 days post-dosing		●	●	●	●	●	●				
Recording of SAEs, AESIs, COVID-19 cases, and pregnancies. In addition, pIMDs and suspected HZ episodes in the HZ/su and mRNA-1273 booster cohort		●	●	●	●	●	●	●	●		
Recording of AEs/SAEs related to study participation, or SAEs related to concurrent GlaxoSmithKline medication/vaccine	●	●	●	●	●	●	●	●	●	To be recorded if the event onset occurs any time after signing the ICF	
Recording of withdrawals		●	●	●	●	●	●	●	●		
Study Conclusion								●			

AE = adverse event; AESI = adverse event of special interest eDiary = electronic diary; HZ= Herpes Zoster; IMC = intercurrent medical condition; PCR = polymerase chain reaction; pIMD = potential immune mediated disease; SAE = serious adverse event

Grey cells indicate the given activity is not planned for the corresponding timepoint(s)

The double-line border following Phone contact 1 indicates an interim analysis

● is used to indicate a study procedure that requires documentation in the individual electronic case report form

○ is used to indicate a study procedure that does not require documentation in the individual electronic case report form

CONFIDENTIAL

217670 (ZOSTER-091)
Protocol Amendment 1 Final

Table 2 Schedule of study intervention administration and blood sampling for the study groups

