- Solicited local events (intensity [any grade, Grade 3], resulting in medically attended visit) during the 7-day follow-up period after each intervention administration will be summarized. Any events ongoing beyond the 7-day post-vaccination period, following each vaccination visit and overall will also be tabulated for each vaccine separately.
- Solicited systemic events (intensity [any grade, Grade 3], and resulting in a medically attended visit) during the 7-day follow-up period after each vaccination visit will be summarized. Any events ongoing beyond the 7-day post-vaccination period, following each vaccination visit and overall will also be tabulated for each vaccine separately.
- The duration of the solicited AEs, both local (for each vaccine separately) and systemic, during the 7-day follow-up period after each vaccination visit and overall (total duration) will be calculated and summarized by mean, median, standard deviation, and range.

9.3.6.2. **Unsolicited AEs**

The number and percentage of participants reporting unsolicited AEs classified by MedDRA primary System Organ Class (SOC) and Preferred Term (PT) will be summarized along with exact 95% CIs during:

- The 14-day post-vaccination period after each and any vaccination visit for all study groups and
- The 30-day post-vaccination period after each and any vaccination visit. It should be noted that participants in the HZ/suSeq and FluD-QIVSeq groups will receive their HZ/su or Flu D-QIV, respectively, at Day 14 post mRNA booster vaccine dose at Day 1.

Unsolicited AEs will also be presented by intensity (any grade and Grade 3), any related, Grade 3 related, Grade 3 non-serious, Grade 3 non-serious related, and resulting in a medically-attended visit.

9.3.6.3. **SAEs**

Number and percentage of participants reporting SAEs and fatal SAEs from first vaccination up to 30 days post-last vaccination and from first vaccination up to study end

will be summarized for all study groups (HZ/suSeq, HZ/suCoAd, FluD-QIVSeq, FluD-QIVCoAd and overall). Any related SAEs will also be presented for all study groups (HZ/suSeq, HZ/suCoAd, FluD-QIVSeq, FluD-QIVCoAd and overall). Fatal SAEs will be presented by onset day and day of death, for both any fatal SAEs and any related fatal SAEs. All SAEs will be summarized by MedDRA SOC and PT. SAEs, fatal SAEs and withdrawals due to SAEs will also be listed.

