- SAEs, pIMDs, AESIs, suspected HZ episodes, IMCs, COVID-19 cases and pregnancies until the Data Lock Point (DLP) for all groups.

No hypothesis testing was conducted as part of the safety IA.

The final analysis will include safety follow-up up to 6 months post the last vaccine dose.

No IA was conducted for the immunogenicity data for either cohort as this data was not available at the timepoints set for the safety and reactogenicity data IA.

12. Changes in the Planned Analysis

Since the immunogenicity results were not available in time, the interim analysis was restricted to safety and reactogenicity data and did not include immunogenicity data as was originally planned per protocol.

The solicited systemic eDiary was unable to be programmed to shut off post-day 7 following vaccination assuming there were no ongoing events reported, which meant that these events were solicited daily for 30 days post-vaccination, even if they were not ongoing after 7 days post-vaccination. Since, as per protocol, any adverse event with an onset more than 7 days and up to 30 days post-vaccination was to be reported as an ‘unsolicited AE’, the AEs meeting this definition entered in the eDiaries were transcribed by the site staff to the unsolicited AE eCRF page and will be subsequently analyzed as such and not counted as solicited AEs in the safety analyses.

In Table 4 of the protocol, interval ranges between certain visits were provided whereby if the visits were to happen beyond these specified intervals, participants may not have been eligible for inclusion in the applicable Per Protocol Set (PPS). The out of window intervals in Table 8 and Table 9 below represent the actual limits that will be used in the final analyses.

Table 8 Intervals between study visits for HZ/su and mRNA-1273 booster cohort

Interval	Planned Visit Interval	Allowed Interval Range to Remain in PPS
		HZ/suSeq group
Pre-vaccination → Visit 1	-7 days	No impact on PPS
Visit 1→Visit 2	14 days	13-49
Visit 1→Visit 3	28 days	25-49
Visit 2→Visit 4	28 days	No impact on PPS
Visit 2→Visit 5	56 days	48-83
Visit 5→Visit 6	28 days	25-49
Visit 5→Phone contact 1	42 days	No impact on PPS

Interval	Planned Visit Interval	Allowed Interval Range to Remain in PPS
Visit 5→Phone contact 2	168 days	No impact on PPS
HZ/suCoAd group		
Pre-vaccination → Visit 1	-7 days	No impact on PPS
Visit 1→Visit 2	28 days	25-49
Visit 1→Visit 3	56 days	48-83
Visit 3→Visit 4	28 days	25-49

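### Under its own duration rule, SAP 9.1.1 counts solicited reactions with more than 7 symptom days, but the protocol asks for those still present after Day 7, so this table can only be understated

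*SAP*

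**What the plan says.** Protocol 9.3.6.1 deals with solicited local and solicited systemic events in separate items and makes the same request in each: "Any events ongoing beyond the 7-day post-vaccination period, following each vaccination visit and overall will also be tabulated for each vaccine separately". The window is set in the protocol's schedule of activities (1.3, Table 1) by "onset post-study intervention administration (day of and following 6 days". It is therefore Days 1-7, with Day 1 the day of vaccination, and Day 8 is the first day beyond it.

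SAP 9.1.1 plans two lines on this subject. For local events it gives "The percentage of subjects with solicited local adverse events lasting longer than 7 days", and for systemic events "The percentage of subjects with solicited systemic adverse events lasting longer than 7 days". Each is paired with the total duration of those events in days and is presented by vaccination visit. Earlier in the same section the SAP defines how length is measured: "duration is calculated as sum of the unique number of days of the solicited AE with greater than zero grade".

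The SAP also states: "Solicited AEs with onset during the 7-day solicitation period that continue beyond the 7-day period will be reported as solicited AEs". Section 12 of the amended SAP records changes to the interim analysis, the systemic eDiary and the visit windows for the per-protocol sets, but nothing on this table. The SAP of 3 December 2021 has the same two lines, and its Section 12 reports no changes from plan.

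**The concern.** The protocol sets a calendar test: is the reaction still there when the window has closed? The SAP, taken with its own duration rule, sets a length test: does the reaction have more than 7 symptom days? The two tests can disagree for any reaction that does not occupy every day from Day 1 onward.

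What is at stake is one descriptive reactogenicity table. Reactogenicity after co-administration is among the data the study is designed to provide (protocol 4.2), and this is the protocol's tabulation of reactions that outlast the window. A reader comparing co-administration with sequential vaccination would take the SAP percentages as the protocol's persistence percentages, which they need not be.

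**Working it through.** The documents state no figure for this table, so there is nothing to reproduce. The check compares the two rules over all possible onset and end days.

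**Inputs.** Onset day s runs from 1 to 7 (protocol Table 1; SAP 9.1.1). The last symptomatic day is e. For an event without gaps, the SAP duration is e - s + 1.

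**Rules.**
- Protocol 9.3.6.1: counted if e ≥ 8.
- SAP 9.1.1, with its duration rule: counted if e - s + 1 > 7, that is, e ≥ s + 7.
- Left out by the SAP but wanted by the protocol: 8 ≤ e ≤ s + 6.

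| Onset day s | Last days left out | First last day counted by the SAP |
|---|---|---|
| 1 | none | 8 |
| 2 | 8 | 9 |
| 3 | 8-9 | 10 |
| 4 | 8-10 | 11 |
| 5 | 8-11 | 12 |
| 6 | 8-12 | 13 |
| 7 | 8-13 | 14 |

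**Example.** Day 3 to Day 9 gives 9 - 3 + 1 = 7 days. The event is present on Days 8 and 9, so the protocol counts it. Seven is not more than 7, so the SAP does not. Day 3 to Day 10 gives 8 days, and both count it.

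**Extent of the disagreement.** For last days 8-14 there are 7 × 7 = 49 onset/end combinations. The SAP rule leaves out 0 + 1 + 2 + 3 + 4 + 5 + 6 = 21 of them, all among the 42 with onset after Day 1. This counts combinations. It is not a share of events or participants.

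**Direction.** Since s ≥ 1, e ≥ s + 7 implies e ≥ 8. Every event counted by the SAP is therefore counted by the protocol, and the reverse error cannot occur.

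**Intermittent events.** Only days with a grade above zero are counted, so an event with onset on Day 1 can also drop out. Symptoms on Days 1, 2, 3, 6, 7, 8 and 9 make 7 symptom days, yet the event is present after Day 7.

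**The case against.** The strongest reply is that the SAP meant the same thing as the protocol. When it describes the diary datasets it separates "events that occurred within the first 7 days and events that occurred longer than 7 days", where the second phrase appears to label the records after Day 7. On that usage, the two lines in 9.1.1 could mean reactions persisting past Day 7 after the visit, and the definitions would agree. The December 2021 SAP's statement that nothing had changed fits that intention.

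This reading is possible but weaker. The lines pair the phrase with total duration in days, which is the quantity the SAP has just defined as a count of symptom days. Where the SAP means the calendar, it says so, as in its rule on events that continue beyond the 7-day period. The mention of the vaccination visit identifies which dose is meant, as it does in the preceding paragraph on duration. If both readings are allowed, two programmers could build different tables, which is itself a reason to settle the text.

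Other parts of the reply stand. Events continuing past Day 7 remain solicited AEs. They appear in the any-grade, Grade 3 and medically attended tables, in the duration summaries and in the individual listings. The table is descriptive and supports no hypothesis.

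Two stronger inferences are tempting and are not supported. One is that every persistent reaction starting after Day 1 is missed. It is not: any such reaction with 8 or more symptom days is counted. The other is a numerical shortfall. If durations were geometric with a mean of 2 or 3 days (an assumption), the proportion of Day 3 onset events lasting past Day 7 that the SAP captures would be (1/2)² = 25% or (2/3)² = 44%. Those figures follow from the assumed distribution and are per event, conditional on onset day. A participant enters the table if any one event qualifies, so they say nothing about the percentage of participants.

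**Conclusion.** The point holds as a low-severity mismatch between protocol and SAP. On the literal reading, the SAP lines omit solicited events with onset on Days 1-7 that are present on Day 8 or later with 7 or fewer symptom days in total. The persistence table can then only be understated, never overstated. The overall tabulation is also missing from these lines, and Section 12 is silent on the difference.

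The conclusion rests on applying the SAP's own duration rule to its own phrase. If the authors intended the calendar meaning, what remains is unclear wording and the missing overall tabulation. The size of any shortfall cannot be estimated from the documents. The primary and secondary hypotheses are unaffected.

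**What to change.** In SAP 9.1.1, define both lines as solicited AEs with onset on Days 1-7 and a grade above zero on Day 8 or later. Tabulate them by vaccination visit, overall, and separately for each vaccine, as protocol 9.3.6.1 states. Episodes that begin after Day 7 stay with the unsolicited AEs, as Section 12 already provides. Where systemic events after co-administration cannot be split by vaccine, present them by visit and record that in Section 12. Keep duration above 7 days only as an additional row.

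The cost is one sentence and one derivation flag. No new data are needed: the diary datasets already hold records past Day 7, and for systemic events Section 12 notes that "these events were solicited daily for 30 days post-vaccination".
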